### **PET Scanning**

18. The N=60 Depressed subjects and N=30 Never-Depressed subjects will undergo a single [18F]DOPA PET scan at baseline.

19. PET experiments will be conducted with the mCT scanner in the PET Suite on the R1 level of the Public Health Building. Subjects participating in the study will be escorted on PET scan day by a research staff member to the R1 level of the Public Health Building where the PET scanner is located. A research staff person will stay with the subject throughout the procedure. The preparation of the subject will include the placement of a venous catheter.

20. The radiochemistry laboratory and PET suite staff will be in frequent communication regarding the status of preparation of the research subject (such as placement of venous line) and the progress of the radiotracer synthesis. [18F]-FDOPA will be produced at the on-site radiochemistry facility. After fasting overnight, participants are pretreated with 150 mg of carbidopa 120 minutes prior to [18F]-FDOPA injection to increase brain bioavailability. As scan time approaches, the subject will be placed in a supine position on the camera table and will have vital signs (blood pressure and heart rate) obtained. Each person's head will be positioned, and a headholder will be used to decrease head movement during the scan. Similar to previous studies, participants will be injected with [18F]-FDOPA (maximum dose of 5 mCi). The emission scan will be initiated with injection and data obtained for 90 minutes. At the completion of the scan the IV catheter will be removed, and the subject will be evaluated (including mental status and vital signs) by a study physician. Vital signs will be performed prior to discharge from the PET suite. A new IND application to the FDA is underway by the PI ([name]) to cover the baseline PET scan in this study and will be added to this application when received.

21. PET data will be reconstructed into images using the appropriate reconstruction protocols and filters. PET images will be coregistered to the MRI and regional time activity curves will be measured. Data will be fitted to pharmacokinetic models, and relevant pharmacokinetic parameters, including the percent of receptors engaged by dopamine, will be estimated based on the model fitting procedures.

### **Clinical treatment**

23. For the mechanistic probe of dopaminergic functioning using LDOPA, a crossover trial will be conducted. In Step 1, participants will be randomized to initially receive either active L-DOPA or matching placebo based on a block design using R Statistical Software version 3.4.3 (R Foundation for Statistical Computing, Vienna, Austria). Participants, physicians and research staff will be blinded to group assignment. The NYSPI Pharmacy will maintain the randomization key for each site and can unblind individual subjects in emergencies. The blind will not be broken until study completion. Following Step 1, participants will have repeat MRI scanning and cognitive/behavioral testing, then undergo a 1 week taper and wash out period before being crossed over to the opposite treatment (Step 2). Repeat cognitive and behavioral testing will occur after Step 2 but there will be no further neuroimaging.

24. Subjects will take active or placebo tablets three times daily (9am, 1pm, 5pm). Those assigned to L-DOPA will begin with a Week 1 L-DOPA daily dosage of 150mg, or 1.5 25mg carbidopa/100mg levodopa

---

tablets at 9am and placebo tablets at 1pm and 5pm. In Week 2 the L-DOPA daily dose will increase to 300mg (1.5 25mg carbidopa/100mg levodopa tablets at 9am and 5pm, with placebo at 1pm), followed by a Week 3 L-DOPA daily dose of 450mg (1.5 25mg carbidopa/100mg levodopa tablets three times daily). Subjects assigned to placebo will take 1.5 placebo tablets three times daily for three weeks. Individuals will be instructed to maintain the same timing of doses throughout the study. Individuals unable to tolerate an increased dose will have their dosage reduced to the maximum previously tolerated dose.

25. Following the three-week Step 1 Phase, there will be a one-week taper period. Subjects will be instructed to decrease their dosage to 1.5 tablets twice daily for 3 days, followed by 1.5 tablets once daily for three days, then discontinue tablets. Subjects will then restart an identical dosing regimen while being crossed over to the opposite treatment assignment for Step 2.

26. At each weekly visit, subjects will meet with a psychiatrist or study physician. Both in our Pilot study and the literature overall, L-DOPA is an extremely well tolerated medication at doses < 600mg, which is substantially less than the doses often reached in the treatment of Parkinson's disease (900-1200mg). L-DOPA has been administered to healthy subjects in single dose studies and found to be well-tolerated. In Parkinson's disease, a recent clinical trial published in the New England Journal of Medicine randomized patients to receive 150mg, 300mg, or 600mg L-DOPA for 40 weeks. No dyskinetic effects or other neuropsychiatric effects were observed that were greater than the placebo group.

27. Participants will be given the option to receive medication reminders via text messages three times daily (morning 9am, midday 12pm, evening 5pm) adhering to the study medication schedule. Text messages will be automatically sent out by service provider [www.remindercall.com](http://www.remindercall.com). Participants will be able to opt-in and opt-out of this service at any time during the study by either replying "STOP" to any text message or by contacting the study coordinator.

26. At the conclusion of Step 2, participants will undergo another 1 week washout phase and then enter post-protocol open treatment, which will be offered for 3 months. Appropriate medication treatment options for depression will be discussed with each participant, which may include continued off-label use of LDOPA as discussed below.

## Assessments

29. Subjects are expected to have a screening/evaluation visit, pre-treatment PET/MRI scanning day(s), and weekly visits during Steps 1 and 2 of the crossover trial (i.e., Weeks 0-3 [Step 1], 4 [taper], 5-8 [Step 2], 9 [taper]). At each clinic visit, depression severity measured using the MADRS and adverse events assessed. The presence of any suicidal thoughts will be assessed at every contact. Vital signs (weight, heart rate, blood pressure) will also be measured.

30. Cognitive assessments will be performed at baseline and after each step of the crossover trial. To obtain a broad assessment of cognitive function, we will administer the NIH Toolbox Cognition Battery that measures 6 ability subdomains and assess episodic memory functioning supplemental NIH Toolbox Auditory Verbal Learning (Rey) Test. Our primary outcome is processing speed, assessed using Coding from the Wechsler Adult Intelligence Scale-IV (WAIS-IV) and the Pattern and Letter Comparison tests (secondary outcomes). To assess executive function, we will supplement the NIH Toolbox with the NIH-

---

EXAMINER battery, which measures working memory, inhibition, set shifting, fluency, insight, planning, social cognition and behavior (secondary outcomes).

31. Gait will be assessed at baseline and after each step of the crossover trial as both a single and dual tasks (ST, DT) using the GaitRite system (Sparta, NJ), which assesses gait parameters in real time (gait speed, cadence, stride length). For the ST (primary gait outcome), participants are instructed to walk at their usual or normal speed over the 15' walking course. For the DT (secondary outcome), participants are instructed to walk at their usual pace while simultaneously verbally listing as many animals as possible (fluency DT). In addition, a counting DT will be used in which participants are instructed to walk at their usual pace while simultaneously performing serial subtractions by threes starting at 100.

32. Other clinical assessments collected each visit include the CGI Severity and Improvement (provide a clinical assessment of subjects at each visit and help maintain safety by identifying clinical worsening), Inventory of Depressive Symptoms—Self Report (IDS-SR) (provide a self-report measure for depressive symptoms), Structured Pill Count Interview (to assess study medication compliance), and the Treatment Emergent Side Effect Scale (TESS) to monitor side effects associated with medication treatment. We will utilize the Unified Parkinson's Disease Rating Scale (UPDRS) to identify any dyskinesias caused by L-DOPA, although based on our previous studies we are not expecting to observe motor side effects with the L-DOPA doses and duration being used in this study.

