## Specific Aims and Hypotheses

### Specific Aims and Hypotheses

The proposed study will enroll 60 elderly depressed outpatients who exhibit evidence of dopaminergic dysfunction, characterized as either slowed processing speed or slowed gait speed. To disentangle depression effects from age-related changes, 30 never-depressed elders also will complete baseline evaluation. Assessments include PET imaging of dopamine synthesis and receptor density, neuromelanin-sensitive MRI (NM-MRI) measurement of nigrostriatal status, task-based MRI focused on effort-based decision making and reward processing, and comprehensive psychiatric, neurocognitive, and physical performance evaluation. Depressed subjects then will be randomized to L-DOPA or placebo for 3 weeks, followed by repeat multimodal MRI and cognitive/behavioral assessments. In a cross-over phase,

---

participants will receive the opposite intervention for an additional 3 weeks followed by clinical and cognitive assessments only. This mechanistic probe allows us to examine the contributions and interrelationships of dopamine-dependent processes in LLD and evaluate the responsivity of dopamine systems to pharmacological stimulation.

**AIM 1:** To characterize dopaminergic dysfunction in LLD at molecular, circuit, and behavioral levels. **Hyp 1:** Compared to age- and gender-matched controls on baseline fMRI, LLD subjects will be less willing to expend effort for rewards and exhibit lower prefrontal cortex (PFC) and striatal activation on the Effort Expenditure for Rewards Task (EEfRT). **Hyp 2:** Across all subjects, lower striatal [18F]-FDOPA relative influx rate (Kocc), lower midbrain & striatal [18F]-fallypride binding, and lower NM-MRI signal in the substantia nigra, pars compacta (SNc) will predict lower performance across RDoC domains: Positive Valence (impaired willingness to expend effort, decreased neural activations on the EEfRT), Cognitive (slowed processing speed and executive dysfunction), and Sensorimotor (slowed gait speed). **Hyp 3:** Across all subjects, slowed processing and gait speed likewise will predict lower willingness to expend effort on the EEfRT.

**AIM 2:** To examine responsivity of dopamine circuits in LLD to stimulation with L-DOPA.

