### Overview

The overarching goal of this project is to characterize the influence of dopaminergic system dysfunction on the clinical presentation of late-life depression (LLD) across multiple Research Domain Criteria (RDoC) domains (Positive Valence Systems, Cognitive Systems, and Sensorimotor Systems) at several levels of analysis (cellular [PET], structure / circuit [MRI], and functional / self-report). This IRB pertains to procedures completed at Columbia/NYSPI. A companion grant in this Collaborative R01 project takes place at Vanderbilt University Medical Center and utilizes similar, but not identical procedures (e.g., the PET scanning at Vanderbilt utilizes a different radiotracer). Thus, we have opted to have separate IRB protocols for this project. At Columbia/NYSPI we will enroll 60 elderly depressed outpatients who exhibit behavioral evidence of dopaminergic dysfunction, defined as either slowed processing speed or slowed gait speed. To disentangle the effects of depression from age-related changes, 30 psychiatrically healthy elders also will complete baseline evaluation. After determination of eligibility, baseline assessments include PET imaging measurements of dopamine synthesis and receptor density, neuromelanin-sensitive MRI measurement of long-term nigrostriatal dopamine transmission, task positive MRI focused on effort-based decision making and reward processing, and a comprehensive psychiatric, neurocognitive, and physical performance evaluation. To examine responsivity of the dopamine system to dopamine supplementation with L-DOPA, the 60 depressed subjects (ONLY) then will be randomized to L-DOPA or placebo for 3 weeks, followed by repeat multimodal MRI, neurocognitive and behavioral assessments. In a cross-over design, participants will then receive the opposite intervention for an additional 3 weeks followed by clinical and cognitive assessments only.

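### The visit calendar runs one week longer than the treatment section: with a three-week Step 2 it implies a two-week gap between steps and ends at Week 9, past the stated eight-week limit on treatment delay

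*Protocol*

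**What the plan says.** Two parts of the Protocol's Study Procedures set out the timing of the crossover.

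- **Clinical treatment, items 23 to 25, and the last item of that section (a second item numbered 26).** After Step 1: "Following the three-week Step 1 Phase, there will be a one-week taper period". Item 23 describes the same interval: participants are rescanned and retested, "then undergo a 1 week taper and wash out period before being crossed over to the opposite treatment (Step 2"). Within that week they "decrease their dosage to 1.5 tablets twice daily for 3 days, followed by 1.5 tablets once daily for three days, then discontinue tablets". Then: "Subjects will then restart an identical dosing regimen while being crossed over to the opposite treatment assignment for Step 2". The titration in item 24 covers Weeks 1, 2 and 3. After Step 2 there is a further one-week washout, and open treatment follows it.
- **Assessments, item 29.** Visits are weekly, at "Weeks 0-3 [Step 1], 4 [taper], 5-8 [Step 2], 9 [taper"].

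Step 2 is given as three weeks in three other places: the Lay Summary, Specific Aims and Hypotheses ("participants will receive the opposite intervention for an additional 3 weeks") and the Overview ("participants will then receive the opposite intervention for an additional 3 weeks").

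Three places give an eight-week figure. End of study procedures (item 33) gives it as the total length of the crossover. Research Related Delay to Treatment, and item 3 under Risks/Discomforts/Inconveniences, give it as the delay before a depression treatment of established benefit.

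The SAP's Aim 2, Hypothesis 1 analysis compares change from baseline to Week 3, which is Step 1 only.

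**The concern.** The treatment section and the visit calendar are both operative instructions, and they cannot both be followed as written. Two things depend on which one staff use.

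- **Washout and assessment timing in the crossover.** The tablet-free time before Step 2 governs how much of the first treatment could carry over. The cognitive and gait testing after Step 2 (Assessments, items 30 and 31) is tied to the day Step 2 ends. Exploratory Aim 2 looks at how long L-DOPA effects last in this phase, so for participants given L-DOPA first, the time off drug is part of what is being studied. If participants are scheduled from different sections, that interval varies between them for no planned reason.
- **Delay to treatment.** The Protocol states a maximum of eight weeks. A schedule whose last taper falls at Week 9 does not fit that limit.

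**Working it through.** This is week arithmetic only. Time is counted from the start of Step 1 dosing, taken as Week 0.

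**Reproducing the stated total.** From Clinical treatment: Step 1 = 3 weeks, taper and washout = 1, Step 2 = 3 (identical regimen), final washout = 1.

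- Step 2 starts at 3 + 1 = Week 4.
- Step 2 ends at 4 + 3 = Week 7.
- Open treatment starts at 7 + 1 = Week 8.
- Total = 3 + 1 + 3 + 1 = 8 weeks, which agrees with the stated eight.

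**Reading the calendar.** The labels are 0-3, 4, 5-8 and 9.

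| Reading of the labels | Gap between steps | Step 2 dosing | Final taper ends |
|---|---|---|---|
| Treatment section, for comparison | 1 week | 3 weeks | Week 8 |
| A. Time points; Week 5 starts Step 2 as Week 0 starts Step 1 | 5 − 3 = 2 weeks | 8 − 5 = 3 weeks | Week 9 |
| B. Time points; Step 2 starts when a one-week taper ends at Week 4 | 4 − 3 = 1 week | 8 − 4 = 4 weeks | Week 9 |
| C. Ordinal weeks, Week 0 being the baseline visit | 1 week | 4 weeks (5, 6, 7, 8) | 3 + 1 + 4 + 1 = 9 weeks |

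If every label is instead a full week, Step 1 has four weeks as well (0, 1, 2, 3), which contradicts its stated three. No reading gives both a one-week gap and a three-week Step 2. Only reading A keeps the three-week Step 2 that the Protocol states directly.

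**Tablet-free days between steps.** The taper takes 3 + 3 = 6 days.

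- One-week gap: 7 − 6 = 1 day.
- Two-week gap (reading A): 14 − 6 = 8 days.

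**Delay to treatment.** Open treatment follows the second washout. That is Week 8 under the treatment section and Week 9 under the calendar, against a stated maximum of 8.

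**What the eight-week figures can settle.** The total in End of study procedures is not decisive by itself: it equals 3 + 1 + 3 + 1, but it also equals the calendar's end of Step 2 if the final taper is left out. The maximum delay is more informative, because open treatment begins only after that last washout.

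**The case against.** The strongest reply is that item 29 is a list of visits, in a parenthesis under Assessments, and prescribes no dose, taper or washout. Dosing is set in Clinical treatment, which is clear and agrees with the eight-week figures. On this view Week 4 was used for the taper visit and Week 5 then repeats the role of Week 0, so the extra week is a numbering slip. The calendar lists four visits for each step, which fits two equal three-week steps. This is a plausible explanation of how the mismatch arose. It does not remove it: the visits are described as weekly, each label is tied to a step, and nothing explains the extra week. Nor does the rescan after Step 1 account for it, since neither section allots a week to scanning.

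A figures file is listed under End of study procedures but was not available here. It may contain a study diagram, which limits certainty that no clear calendar exists. It would not correct the text of item 29.

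A reader might infer more than the documents support:

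- **That Step 2 lasts four weeks, a third longer than Step 1.** This follows only from readings B and C of the visit labels. No section states it, three sections state three weeks, and the titration has no fourth week.
- **That the main L-DOPA comparison is compromised.** It ends at Week 3, before the two schedules diverge.
- **That a planned durability analysis is affected.** The SAP contains none; durability appears only as Exploratory Aim 2.
- **That all 60 depressed participants are affected.** Only those who reach Step 2 are.
- **That the longer gap would change a result.** No figure in the documents shows that 1 versus 8 tablet-free days would do so.

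**Conclusion.** The inconsistency holds. The calendar runs one week longer than the treatment section: Week 9 against Week 8. Taking Step 2 as three weeks, that week falls between the steps, giving a gap of two weeks rather than one and about 8 rather than 1 tablet-free days. The end of the schedule then exceeds the stated maximum treatment delay by one week.

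The day counts assume that the taper starts as soon as Step 1 dosing ends and that nothing is taken after its sixth day. The comparison with the eight-week limit assumes that the delay is counted from Week 0.

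The importance is moderate. The SAP's Aim 2 test is untouched. What is exposed is the exploratory crossover phase, through washout and the timing of the post-Step-2 assessments, and the accuracy of the delay described for depressed participants. The documents do not establish which schedule is intended.

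**What to change.** Reconcile the Overview, Clinical treatment (items 23 to 25 and the closing item on washout and open treatment), Assessments (item 29), End of study procedures (item 33), Research Related Delay to Treatment, and item 3 under Risks/Discomforts/Inconveniences into one calendar. It should give, by day or week:

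- the end of Step 1 dosing;
- the taper days and the tablet-free days;
- the start and end of Step 2 dosing;
- the post-Step-2 assessment;
- the second taper or washout and the start of open treatment.

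If the longer calendar is the intended one, restate the eight-week total and the eight-week maximum delay to match. The choice of schedule is the sponsor's.

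The cost is a change of Protocol wording. The SAP's Aim 2 analyses need no change on this account.

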### End of study procedures

33. Following the 8 week (in total) duration crossover study, endpoint assessments of psychiatric symptoms, cognition, and motor functioning will be made. Once post-treatment research procedures are completed, patients will enter 3 month open treatment period provided free of charge as described below.

You can upload charts or diagrams if any

Figures.pdf

Dosimetry chart for [18F]DOPA.pdf

### Criteria for Early Discontinuation

#### Criteria for Early Discontinuation

The risk of non-response or adverse events to L-DOPA during the study period is addressed by having close clinical follow up of study subjects and stringent withdrawal criteria. These criteria are (1) participant withdraws his or her consent; (2) **significant clinical worsening (in any aspect, including motoric function or depressive symptoms) as defined by a CGI-Improvement scale of 6 (worse) or 7 (much worse) for 2 consecutive visits**; or (3) development of significant side effects or an adverse event. Any subjects meeting any of these criteria will be withdrawn from the study and treated clinically. Furthermore, subjects may be withdrawn if they repeatedly miss scheduled appointments or clinical worsening necessitates more intensive treatment. No treatment is currently available for slowing, so there is not a standard of care treatment to offer patients withdrawn from the study. Thus, withdrawn patients will be followed in the open treatment period, offered appropriate psychiatric treatments if they have any conditions requiring treatment (e.g., depression), and be referred to their internist for close medical follow up.

## **Blood and other Biological Samples**

Please create or insert a table describing the proposed collection of blood or other biological specimens  
A 20cc blood sample will be drawn from all depressed (N=60) and healthy (N=30) subjects baseline.  
General medical tests will be performed as safety screens for Depressed subjects, such as CBC, Chem 7, LFTs, TSH, cholesterol, B12, and folate. Also, plasma samples from all subjects (Depressed and Never-Depressed) will be isolated by centrifugation at 1000 x g for 10 minutes at 4C, aliquoted into siliconized polypropylene tubes and stored at -80C until batch assay. Samples will be shipped to Co-Inv [name]'s laboratory at Emory University in batches by a staff member at each site who is certified to ship biospecimens using standard procedures for shipping samples on dry ice and with arrival the next day before 10am via Fedex.

## **Assessment Instruments**

Create a table or give a brief description of the instruments that will be used for assessment

Structured Clinical Interview Diagnostic for DSM 5 (SCID): this semi-structured diagnostic interview will allow determination of whether subjects meet selection criteria.

Cumulative Illness Rating Scale-Geriatric (CIRS-G) will be filled out at baseline to measure chronic medical illness burden.

Subjects' current physical pain will be assessed weekly using a 100mm Pain Visual Analog Scale (VAS) and used as a covariate in analyses of gait speed.

MMSE: standard means of assessing global cognition. The SCID, CES-D, and MMSE will be measured at baseline for the purpose of subject selection, while the following measures will be collected weekly throughout the study.

Montgomery Asberg Depression Rating Scale: standard measure of depression severity that measures changes in depressive symptoms.

CGI Severity and Improvement: scales measuring the clinician's view of subjects' global functioning that will provide a clinical assessment of subjects at each visit and help maintain safety by identifying clinical worsening.

Structured Pill Count Interview: assessment of study medication compliance accounting for each dose of prescribed study medication during the study period.

Blind Assessments rate clinician's and patient's guesses as to study drug assignment.

Unified Parkinson's Disease Rating Scale (UPDRS): standardized, reliable, and valid instrument for

---

assessing the severity of the clinical features of PD; questions 32 and 33 will be used in this study to assess the duration and disability of dyskinésias caused by L-DOPA. While we include this measure, we are not expecting to observe dyskinésias in healthy subjects or at the L-DOPA doses being used in this study. Typically, such L-DOPA side effects emerge only in patients who have had Parkinson's disease for a number of years and then only if the LDOPA dose is raised to 600 mg or more.

Treatment Emergent Side Effect Scale: standardized general checklist used in our clinic for monitoring side effects associated with medication treatment.

Inventory of Depressive Symptoms—Self Report (IDS-SR): rating scale for depressive symptoms based on DSM criteria that has been increasingly used in antidepressant studies due to its equivalent weightings for each item, understandable anchor points, and inclusion of all DSM criteria.

Processing speed will be assessed using the Digit Symbol test from the Wechsler Adult Intelligence Scale-III (WAIS-III) and the Pattern and Letter Comparison tests. These tests are all reliable and valid, with moderate to high loadings on the latent speed factor.

To broadly assess cognitive function, we will administer the NIH Toolbox Cognition Battery, a brief and psychometrically sound set of 7 computerized instruments providing an overall cognitive index from measures of 6 cognitive domains. We also include the supplemental NIH Toolbox Auditory Verbal Learning (Rey) Test for a robust assessment of episodic memory and allow for classification of amnestic mild cognitive impairment.

Executive function will be assessed via the NIH-EXAMINER battery designed to assess executive functions reliably, comprehensively, and efficiently. This battery examines working memory, inhibition, set shifting, fluency, insight, planning, social cognition and behavior.

Gait will be assessed as both a single and dual task (ST, DT) using the GaitRite system (Sparta, NJ), which assesses gait parameters in real time (gait speed, cadence, stride length). For the ST, patients are instructed to walk at their usual or normal speed over the 15' walking course. For the DT, patients are instructed to walk at their usual pace while simultaneously verbally listing as many animals as possible (fluency DT). In addition, a counting DT will be used in which patients are instructed to walk at their usual pace while simultaneously performing serial subtractions by threes starting at 100. Patients will start and end at a point 2 meters from the GaitRite mat to eliminate acceleration and deceleration effects. Each ST and DT will be assessed two times with the average used in the analyses. The ST assessment of walking speed in m/s will be the primary gait outcome measure for this study.

Pittsburgh Fatigability Scale (PFS) will assess mental and physical fatigability.

Short Physical Performance Battery (SPPB) provides a performance measure of gait, balance, and lower extremity strength.

The Falls Efficacy Scale-International will assess subjects' fear of falling using a 16-item scale rating respondents' confidence (1 not at all concerned—4 very concerned) in doing daily tasks without falling.

Please attach copies, unless standard instruments are used

